## 8.4 Overdose

For this study, any dose of benralizumab greater than 30 mg within 4 weeks will be considered an overdose. As benralizumab is given by a healthcare professional in a medical setting, an overdose is unlikely to occur.

- An overdose with associated AEs is recorded as the AE diagnosis/symptoms on the relevant AE modules in the eCRF and on the Overdose eCRF module.
- An overdose without associated symptoms is only reported on the Overdose eCRF module.

If an overdose on an AstraZeneca study intervention occurs in the course of the study, the investigator or other site personnel must inform appropriate AstraZeneca representatives immediately, but **no later than 24 hours** of when he or she becomes aware of it.

The designated AstraZeneca representative works with the investigator to ensure that all relevant information is provided to the AstraZeneca Patient Safety data entry site **within one or 5 calendar days** for overdoses associated with an SAE (see [Section 8.2.4](#)) and **within 30 days** for all other overdoses.

There is no specific treatment for an overdose with benralizumab. If overdose occurs, the patient should be treated supportively with appropriate monitoring as necessary.

## 8.5 Human Biological Samples

Instructions for the collection and handling of biological samples will be provided in the study- specific laboratory manual. Samples should be stored in a secure storage space with adequate measures to protect confidentiality. For further details on Handling of Human Biological Samples see [Appendix C](#).

### **8.5.1 Pharmacokinetics**

Pharmacokinetic parameters will not be evaluated in this study.

### **8.5.2 Immunogenicity Assessments**

Immunogenicity assessments will not be done in this study.

### **8.5.3 Pharmacodynamics**

Pharmacodynamic parameters will not be evaluated in this study.

## **8.6 Collection of Human Biological Sample Biomarkers**

Biomarkers will not be evaluated in this study.

## **8.7 Collection of Optional Genomics Initiative Sample**

Optional Genomics Initiative research is not applicable to this study.

## **8.8 Health Economics OR Medical Resource Utilisation and Health Economics**

Health Economics/Medical Resource Utilisation and Health Economics parameters will not be evaluated in this study.

## 9 STATISTICAL CONSIDERATIONS

### 9.1 Statistical Hypotheses

There is no statistical hypothesis to be tested in this study.

### 9.2 Sample Size Determination

The primary objective of this study is to assess safety and tolerability of benralizumab in adult (18 to 75 years of age) male or female patients who have severe asthma with eosinophilic phenotype requiring high dose of ICS and LABA. Based on the literature review, the below table is created for listing the key AEs (headache, pyrexia, pharyngitis and injection site reactions) and hypersensitivity reactions (e.g. anaphylaxis, angioedema, urticaria, urticaria papular, rash) which were included in the USPI, SmPC and the India PI, all in the range of 1% to 10%.

Key AE Terms	Incidence Rate (%)		
	SmPC/ India label	USPI	SIROCCO
Headache	Common (1%-10%)	8%	7%-9%
Pharyngitis		5%	4%-6%
Pyrexia		3%	3%-4%
Injection site reactions		2.2%	2%-4%
Hypersensitivity		3%	3%

$$\text{effectiveness } n = \frac{z^2 p (1-p)}{d^2}$$

where n = calculated sample size, Z = tabulated Z statistic value for  $\alpha$  level of confidence, P = expected proportion of AEs and d = absolute precision level (half-width of the confidence interval [CI]).

Considering the maximum limit of the incidence rate of AEs to be 10%, approximately 139 evaluable participants will be required to present 95% CI around the estimated AE incidence rate with absolute precision level of 0.05. Considering dropout rate of 5%, a total of 147 participants will be required to be enrolled into the study.

### 9.3 Populations for Analyses

For purpose of analysis, the following populations/analysis sets are defined, as presented in [Table 4](#)

**Table 4** **Populations for Analysis**

Population/Analysis set	Description
Enrolled	"Enrolled" means a participant's, or their legally authorised representative's, agreement by signing the ICF to participate in a clinical study following completion of the informed consent process.
Assigned to study intervention	Potential participants who fulfil the eligibility criteria and are assigned with the study identification number.
Evaluable	All participants assigned to study intervention and receiving at least 1 dose of study intervention and provide at least one post baseline assessment.
Safety	All participants assigned to study intervention and who take at least 1 dose of study intervention.

Abbreviation: ICF= Informed Consent Form

## **9.4 Statistical Analyses**

The statistical analysis plan (SAP) will be finalised before data base lock. It will include a more technical and detailed description of the statistical analyses described in this section. This section is a summary of the planned statistical analyses of the most important endpoints including primary and key secondary endpoints.

### **9.4.1 General Considerations**

Statistical analyses will be primarily descriptive in nature. All tabulations, figures, and listings will be produced using the Statistical Analysis Software (SAS) System (Version 9.2 or higher). Data from all participating sites will be pooled for analysis. Standard method of imputation will be applied for any missing/ partial dates.

According to the objectives, the relevant parameters will be summarised descriptively with appropriate statistical methods: categorical variables will be presented using frequencies, percentages and corresponding 95% CI (using Clopper-Pearson exact method, where appropriate) and continuous variables using number of observations, arithmetic mean, standard deviation (SD), median, 25th and 75th percentiles, and minimum and maximum values. The last measurement prior to first dose of study treatment will serve as the baseline measurement.

The safety parameters including AEs, SAEs, deaths, treatment discontinuation/modification, patient discontinuation, laboratory data, etc. will be reported using safety analysis set.

The time-to-event endpoint will be summarised using Kaplan-Meier (KM) method along with the corresponding 95% CIs (as appropriate) and the KM curve will be plotted.

## 9.4.2 Safety

### 9.4.2.1 Primary Endpoints

In order to assess safety and tolerability of benralizumab in participants with severe eosinophilic asthma, following results will be presented:

Frequency, percentage, and 95% CIs (using Clopper-Pearson exact method) will be reported for the following:

- AEs
- SAEs
- TEAEs
- Participants with unexpected Adverse Drug Reactions (ADRs)
- Participants with AEs that lead to study treatment discontinuations or modifications.

The AE profiles in participants will be presented as summaries showing the number of participants (n, %) along with number of events by System Organ Class and Preferred Terms assigned to the event by Medical Dictionary for Regulatory Activities (MedDRA) for the following:

- TEAEs
- SAEs
- Related and non-related TEAEs
- Serious and non-serious TEAEs
- TEAEs based on severity (Mild, Moderate, Severe)
- Unexpected ADRs based on severity (Mild, Moderate, Severe)

The physical examination, vital signs, and laboratory parameters (if available) will be summarised descriptively for actual values and change from baseline values for each visit using the number of observations, arithmetic mean, SD, median, 25th and 75th percentiles, and minimum and maximum values.

### 9.4.2.2 Other Safety Endpoints

None

## 9.4.3 Effectiveness

In order to assess effectiveness of benralizumab in participants of severe asthma of eosinophilic phenotype, following results will be presented using Evaluable Analysis Set:

Annualised exacerbation rate per 24-week period will be reported as percentage, and 95% CI (exact Poisson method), and will be presented in the SAP.

The proportion of participants with  $\geq 1$  asthma exacerbation during the study period will be described using the frequency and the percentage. The proportion of such participants will be calculated as: (number of participants with  $\geq 1$  asthma exacerbation during the 24 week study period)/(total number of participants in the study).

Overall investigator's assessment on the outcome of study treatment will be summarised using frequency and percentage.

Time from first dose of study treatment to the first asthma exacerbation will be calculated as follows: Start Date of first asthma exacerbation minus Date of first dose of study treatment plus 1. The time to first asthma exacerbation for participants who do not experience an asthma exacerbation during the study period will be censored at 24 weeks, or at the time point after which an exacerbation could not be assessed (for lost-to-follow-up participants). The data will be summarised through median time to the first asthma exacerbation along with the 95% CI of median (as per availability of data) and displayed graphically using a KM plot.

The absolute values of blood eosinophil levels and the change from baseline at Week 4, Week 16, and Week 24 will be summarised descriptively using number of observations, arithmetic mean, SD, median, 25th and 75th percentiles, and minimum and maximum values.

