## **DISCONTINUATION OF STUDY INTERVENTION AND PARTICIPANT DISCONTINUATION/WITHDRAWAL**

### **7.1 Discontinuation of Study Intervention**

It may be necessary for a participant to permanently discontinue (definitive discontinuation) the study intervention. If study intervention is permanently discontinued, the participant will remain in the study to be evaluated for safety and effectiveness parameters. Evaluations and safety assessments at the time of discontinuation of study intervention may be performed as per study physician discretion.

Note that discontinuation from study intervention is NOT the same thing as a withdrawal from the study. Participants will be discontinued from benralizumab in the following situations:

- Participant is free to discontinue treatment at any point of time, without prejudice to further treatment (see [Section 7.2](#))
- Development of any study-specific criteria for discontinuation:
  - a. anaphylactic reaction to benralizumab requiring administration of epinephrine
  - b. development of helminth parasitic infestations requiring hospitalisation
  - c. intensive care unit admission with prolonged intubation and mechanical ventilation for asthma-related event
- Severe non-compliance to study protocol including if any dose of benralizumab is missed during the course of the study
- Eligibility requirement found not to be fulfilled (see [Section 5.1](#), [Section 5.2](#))
- Pregnancy (see [Section 8.2.5](#))
- Lost to follow-up

Before a decision to discontinue a participant from benralizumab instituted, the investigator should carefully consider whether continuation on benralizumab or discontinuation of benralizumab will be in the best interest of the patient, and whether the issue can be mitigated by postponing or skipping the dose. It is highly recommended that the AstraZeneca study physician be consulted before the benralizumab discontinuation transaction takes place. In case of safety concerns benralizumab administration may be immediately withheld until the final decision is made.

See the SoA for data to be collected at the time of intervention discontinuation and follow-up and for any further evaluations that need to be completed.

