## 7.2 Participant Withdrawal From the Study

- A participant may withdraw from the study at any time at his/her own request, or may be withdrawn at any time at the discretion of the investigator for safety, behavioural, compliance, or administrative reasons. This is expected to be uncommon.
- A participant who considers withdrawing from the study must be informed by the investigator about modified follow-up options (eg, telephone contact, a contact with a relative or treating physician, or information from medical records).
- If the participant withdraws consent for disclosure of future information, the Sponsor may retain and continue to use any data collected before such a withdrawal of consent.
- If a participant withdraws from the study, it should be confirmed if he/she still agrees for existing samples to be used in line with the original consent. If he/she requests withdrawal of consent for use of samples, destruction of any samples taken and not tested should be carried out in line with what was stated in the informed consent and local regulation. The investigator must document the decision on use of existing samples in the site study records and inform the Sponsor.

Discontinuation of specific sites or of the study as a whole are handled as part of [Appendix A](#).

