## 7.3 Lost to Followup

Participant is considered lost to follow-up when any of the following attempts of contact have failed: 3 attempts of telephone calls, faxes, or emails; having sent 1 certified mail; one unsuccessful effort to check the vital status of the participant using publicly available sources, if allowed by local regulations.

At that visit, participants should be encouraged to remain in the study to complete all subsequent study visits, procedures and assessments or alternatively agree to be contacted by phone calls at monthly intervals to collect AEs/SAEs, changes in concomitant medication, health care utilisation, and asthma exacerbation information.

Reasons for withdrawal of benralizumab should be recorded in the eCRF.

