## **A 9      Study and Site Start and Closure**

The study start date is the date on which the clinical study will be open for recruitment of participants.

The first act of recruitment is the first site initiation visit (SIV) and will be the study start date.

The sponsor designee reserves the right to close the study site or terminate the study at any time for any reason at the sole discretion of the sponsor. Study sites will be closed on study completion. A study site is considered closed when all required documents and study supplies have been collected and a study-site closure visit has been performed.

The investigator may initiate study-site closure at any time, provided there is reasonable cause and sufficient notice is given in advance of the intended termination.

Reasons for the early closure of a study site by the sponsor or investigator may include but are not limited to:

- Failure of the investigator to comply with the protocol, the requirements of the IRB/IEC or local health authorities, the sponsor's procedures, or GCP guidelines
- Inadequate recruitment of participants by the investigator
- Discontinuation of further study intervention development

If the study is prematurely terminated or suspended, the sponsor shall promptly inform the investigators, the IECs/IRBs, the regulatory authorities, and any CRO(s) used in the study of the reason for termination or suspension, as specified by the applicable regulatory requirements. The investigator shall promptly inform the participant and should assure appropriate participant therapy and/or follow-up.

Participants from terminated sites will be discontinued from the study and will be provided with standard of care as determined appropriate by the study investigator.

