6.3.2 Secondary Endpoint Analysis

All Secodary Endpoints will be summarized based on the Evaluable Analysis Set.

Descriptive summaries will be provided for the Asthma Exacerbation. All the continuous variables will be summarized by n, mean, standard deviation, minimum, median and maximum values. All the categorical variables will be summarized as frequency, percentage of Patients in each category and corresponding 95% CI (using Clopper-Pearson exact Method, where appropriate).

Time from first dose of study treatment to the first asthma exacerbation will be calculated as follows: Start Date of first asthma exacerbation minus Date of first dose of study treatment plus 1. The time to first asthma exacerbation for participants who do not experience an asthma exacerbation during the study period will be censored at 24 weeks, or at the time point after which an exacerbation could not be assessed (for lost-to-follow-up participants). The data will be summarised through median time to the first asthma exacerbation along with the 95% CI of median (as per availability of data) and displayed graphically using a KM plot.

Blood Eosinophils level will be summarized based on the Evaluable Analysis Set.

Blood Eosinophils will be summarised descriptively for actual values and change from baseline at week 4, 16, 24 using the number of observations, arithmetic mean, SD, median, 25th and 75th percentiles, and minimum and maximum values.

The Blood Eosinophils in this study is to evaluate the change from baseline to Post-baseline will be analysed using Paired t – test / Wilcoxon signed-rank test at 5% level of significance.

Change from baseline will be determined as:

Change from Baseline = (Post-baseline – Baseline)

Percent Change Change from Baseline = ([Post-baseline – Baseline] / Baseline) X 100

Overall Investigators Assessment will be summarized based on the Evaluable Analysis Set.

Descriptive summaries will be provided for the Overall Investigators Assessment.

Document Title:	Document ID:	BP04-01
Statistical Analysis Plan	Version Number:	3.1
	Effective Date:	25-Nov-2021

All the categorical variables will be summarized as frequency, percentage of Patients in each category and corresponding 95% CI (using Clopper-Pearson exact Method, where appropriate).

7. References

1. ICH E3 Guideline_International Council for Harmonisation

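### Time to first exacerbation: only lost-to-follow-up participants may be censored early, so other unassessed leavers count as exacerbation-free to Week 24, and no Week 24 Kaplan-Meier estimate is planned

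*Protocol*

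**What the plan says.** Protocol 9.4.3 and SAP 6.3.2 give the same censoring rule: participants without an exacerbation "will be censored at 24 weeks, or at the time point after which an exacerbation could not be assessed (for lost-to-follow-up participants"). Protocol 8.3.1 likewise shortens follow-up time only for a participant lost to follow-up. No section gives a censoring date for anyone who leaves for another reason.

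The protocol keeps these ways of stopping apart:

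- **Loss to follow-up (7.3):** "Participant is considered lost to follow-up when any of the following attempts of contact have failed".
- **Withdrawal (7.2):** "A participant may withdraw from the study at any time at his/her own request". The investigator may also withdraw a participant. Anyone considering withdrawal "must be informed by the investigator about modified follow-up options".
- **Site closure (Appendix A 9):** "Participants from terminated sites will be discontinued from the study".
- **Stopping the drug only (7.1):** "the participant will remain in the study to be evaluated for safety and effectiveness parameters".

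Protocol 7.3 also offers the alternative of being "contacted by phone calls at monthly intervals to collect AEs/SAEs, changes in concomitant medication, health care utilisation, and asthma exacerbation information". The disposition shell, SAP Table 14.1.1.1, lists patient decision, adverse event, severe non-compliance, disease progression, pregnancy and other reasons separately from loss to follow-up.

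On output, SAP 6.3.2 states: "The data will be summarised through median time to the first asthma exacerbation along with the 95% CI of median", with a KM plot. The KM block of Table 14.2.2 has rows for the median and its 95% CI only.

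**The concern.** KM estimation relies on each participant staying in the risk set only while an event could have been recorded. Under the literal rule, an event-free participant who withdraws consent at Week 6 and is not assessed again stays in the risk set to Day 168. The later risk sets are then too large and the curve sits too high. The error can only run one way, towards fewer exacerbations.

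The rule also conflicts with the other exacerbation endpoint. The footnote to SAP Table 14.2.1.3 divides each patient's exacerbations by the days that patient took part, which is actual follow-up. The same leaver would have a short follow-up for the annualised rate and a full 168 days for time to first exacerbation.

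The output has a related gap. If fewer than half of participants have an exacerbation by Week 24, the median is not reached and Table 14.2.2 holds no KM estimate with a CI. The planned crude proportion does not fill the gap: Protocol 9.4.3 divides by all participants, so unassessed leavers count as event-free there too.

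**Working it through.** **1. How many could be affected.** The footnote to SAP Table 14.1.1.1 gives 154 enrolled/screened, 10 screen failures, 124 completions, 20 discontinuations, 6 eligible but undosed and 138 analysed. The counts reconcile: 154 − 10 = 144 = 124 + 20, and 144 − 6 = 138. If the 6 undosed are among the 20 discontinuations, 20 − 6 = 14 analysed participants left early (14/138 = 10.1%, against the 5% planned in Protocol 9.2). Under Protocol 4.4, completion means attending the Week 24 visit, so non-completers lack it. The documents do not split the 14 by reason, so the number affected is between 0 and 14.

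**2. Assumptions.** The documents give no on-treatment rate and no exit times. I take a constant rate r of 0.5 to 2.0 per year. The upper value is the minimum entry history (at least 2 exacerbations in 12 months, Protocol 5.1), and Protocol 2.3.2 expects fewer on treatment. Exits are spread evenly over 168 days and are unrelated to exacerbation risk.

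**3. Week 24 risk, true and as written.** Let a = r × 168/365.

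- True risk: P = 1 − exp(−a).
- Chance that a leaver has an event before an evenly spread exit: L = 1 − (1 − exp(−a))/a.
- Rule as written, all 14 affected: W = (124 × P + 14 × L)/138.

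At r = 1.0: a = 0.4603, P = 36.9%, L = 19.9%, so W = (124 × 0.369 + 14 × 0.199)/138 = 35.2%.

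| Rate per year | True risk P | As written W | Understated, 14 affected (points) | 7 affected | 4 affected |
|---|---|---|---|---|---|
| 0.5 | 20.6% | 19.6% | 1.00 | 0.52 | 0.30 |
| 0.7 | 27.5% | 26.2% | 1.32 | 0.68 | 0.40 |
| 1.0 | 36.9% | 35.2% | 1.73 | 0.89 | 0.52 |
| 1.5 | 49.9% | 47.6% | 2.24 | 1.16 | 0.67 |
| 2.0 | 60.2% | 57.6% | 2.59 | 1.34 | 0.78 |

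The last two columns censor the remaining leavers correctly and come from numerical integration of the large-sample KM estimate. With none affected the bias is 0. The Greenwood 95% half-width over these rates is 6.9 to 8.6 points.

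**4. Sensitivity to exit time.** A separate simulation had all 14 leave event-free at Day 28, 56 or 84. The two rules then differed by 0.5 to 0.9 points at a true risk of 10%, 1.6 to 2.6 at 30% and 3.0 to 4.5 at 50%. The figures in step 3 are therefore a ceiling only for evenly spread exits.

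**5. What KM adds under the rule as written.** If no leaver was lost to follow-up, nobody is censored before Day 168. The product-limit estimate of risk at Day 168 then reduces to events/138, the crude proportion, so KM makes no adjustment for early exit.

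**6. Whether the median is reached.** It falls by Day 168 only if r is at least ln 2/(168/365) = 0.693/0.460 = 1.51 per year. Simulated with 138 participants, 14 evenly spread exits and correct censoring, the chance of reaching it is about 0% at 1.0 per year, 8% at 1.25, 48% at 1.5 and 99% at 2.0.

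**The case against.** The strongest reply is that the operative test is when an exacerbation could no longer be assessed, and that the bracket merely names the usual case. The footnote to Table 14.2.1.3 supports this, since it shows an intention to use actual follow-up. Protocol 7.3 also uses its own term loosely. On that reading there is no bias. This stands as a possible reading, but neither document says so. A programmer following the text could censor a withdrawn participant at Day 168 and be within the rule.

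The number affected may also be small or zero. Participants who only stop the drug stay in the study, and those considering leaving are offered modified follow-up or monthly calls. They are rightly kept at risk while assessed. This stands, and it is why 14 is an upper limit.

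On the median, the plan anticipates limited data. The KM curve will be plotted, the proportion with at least one exacerbation is planned, and Table 14.2.1.1 gives per-visit percentages with exact CIs. None of these is a KM estimate at Week 24 with a CI. The shell for Table 14.2.1.2 is not in the text available, so that table could not be checked.

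Finally, the endpoint is secondary, the study is descriptive with no hypothesis, and the bias is small beside the CI. All of that is right and limits the weight of the point.

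**Conclusion.** The concern holds. As written, the rule credits unassessed leavers with exacerbation-free time to Week 24 unless they were lost to follow-up, and it conflicts with the follow-up time used for the annualised rate. With evenly spread exits, the Week 24 risk is understated by 1.0 to 2.6 points if all 14 are affected, by 0.5 to 1.3 if 7 are, and by 0.3 to 0.8 if 4 are. It is 0 if all 14 were lost to follow-up or assessed to Week 24. Exits that are mostly early could make it larger.

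These figures rest on assumed rates and exit times and on placing the 6 undosed among the 20 discontinuations. The direction does not depend on the assumed rates or exit times. Separately, below about 1.5 exacerbations per year the planned table is likely to hold no KM estimate. The change should be made, but it does not threaten the primary safety objective. Confidence is medium, because the intended meaning of the bracket is unknown.

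**What to change.** In SAP 6.3.2, remove the restriction to lost-to-follow-up participants. Censor every event-free participant at the earlier of Week 24 and the last exacerbation assessment or contact, whatever the reason for leaving. State that those who only stop the drug, or who accept modified follow-up, stay at risk while they are assessed.

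Add to Table 14.2.2 the KM probability of at least one exacerbation by Week 24 with its 95% CI, and keep the median for use if it is reached.

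The cost is one reworded sentence and one extra line from the same KM procedure, with no new data. The reported Week 24 risk may rise slightly, within the range given above. Because the SAP already quotes disposition counts, the change should be dated and recorded as a clarification.

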### **8.1.3 Clinical Safety Laboratory Assessments**

Blood and urine samples for determination of clinical chemistry, haematology, and urinalysis will be collected at screening and at EOS (Day 168±7) as indicated in the SoA.

Clinical chemistry will include serum alkaline phosphatase, alanine aminotransferase, aspartate aminotransferase, gamma glutamyl transferase, lactate dehydrogenase, total protein, total bilirubin, albumin, and serum creatinine. Haematology will include haematocrit, leucocyte count, leucocyte differential count (absolute count), platelet count, and haemoglobin. Urinalysis (dipstick) will assess urine haemoglobin/erythrocytes/blood, protein/albumin, and glucose.

Additional safety samples may be collected if clinically indicated at the discretion of the investigator. The date, time of collection, and results (values, units, and reference ranges) will be recorded on the appropriate eCRF.

The clinical chemistry, haematology, and urinalysis will be performed at a local laboratory at or near the investigator site. Sample tubes may vary depending on laboratory method used and routine practice at the site.

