Maximum follow-up time for a participant is approximately 24 weeks; defined as the time from enrolment to the date of EOS visit. For a participant lost to follow-up, this will be defined as the time from enrolment to the time point after which an exacerbation could not be assessed, (ie, the last contact date). Any exacerbations after this time point will not be included in analyses.

Proportion of participants with  $\geq 1$  asthma exacerbation(s) between baseline and end of study will be summarised.

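### Event-free participants are censored at a fixed 24 weeks while event times have no stated cap, so a first exacerbation after Day 168 could take the Kaplan-Meier curve to zero and print a spurious median

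*Protocol*

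**What the plan says.** Protocol 9.4.3, repeated in SAP 6.3.2, gives two rules for time to first exacerbation.

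- Event time is "Start Date of first asthma exacerbation minus Date of first dose of study treatment plus 1". No upper limit is attached.
- Participants without an event "will be censored at 24 weeks, or at the time point after which an exacerbation could not be assessed". The second option is reserved for those lost to follow-up, so an event-free completer gets 24 weeks whatever the date of the last visit.

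Protocol 8.3.1 describes follow-up differently: "Maximum follow-up time for a participant is approximately 24 weeks; defined as the time from enrolment to the date of EOS visit". It also says that the proportion with at least one "asthma exacerbation(s) between baseline and end of study will be summarised". Table 1 schedules an exacerbation assessment at the EOS visit. The timing of that visit appears in 8.1.3, where laboratory samples "will be collected at screening and at EOS (Day 168±7) as indicated in the SoA", that is, Days 161 to 175.

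The endpoint is reported as a Kaplan-Meier median, with its 95% CI when the data allow, and as a curve (SAP Table 14.2.2 and Figure 14.2.1).

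**The concern.** Events and censoring do not share a horizon. Event-free completers all leave the risk set at Day 168, while a participant whose first event falls between Day 168 and the EOS visit stays in with the true event day. After Day 168 the risk set then contains only people selected because they have an event. The last of them must take the estimate to 0, however many others finished without an exacerbation.

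At stake is the summary of the first-listed secondary endpoint. A curve that ends at zero says that everyone exacerbated. A median of about 171 days says that half did so within the study. Neither would be true if most participants were event-free. In the other direction, completers seen on Days 161 to 167 are credited with up to 7 event-free days that nobody observed.

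**Working it through.** **Inputs.** The SAP footnote to Table 14.1.1.1 gives 124 completers, 20 discontinuations, 6 participants never dosed and an analysis set of 138. Dosed non-completers are therefore 138 − 124 = 14. EOS is Day 168±7 (Protocol 8.1.3). The documents give no exacerbation rate and no distribution of visit dates, so both are assumed below. They also give no figure for this Kaplan-Meier analysis. Their one computed design figure is the sample size, which reproduces and is not in dispute: 1.96² × 0.10 × 0.90 / 0.05² = 138.3, rounded up to 139, and 139/0.95 = 146.3, rounded up to 147.

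**Step 1: simplest example.** Take 138 participants with 33 first events by Day 165, one on Day 171, and 104 event-free participants censored at Day 168. With no earlier censoring, S(165) = 105/138 = 0.761. On Day 171 one person is at risk and has the event, so S = 0.761 × (1 − 1/1) = 0. The printed median is 171 days, although 104 of 138 never had an event.

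**Step 2: with the 14 early leavers.** Censor them before Day 160, place 28 events by Day 160 and one on Day 171. S(168) = 0.785.

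| Rule | At risk on Day 171 | S after Day 171 | Median |
|---|---|---|---|
| As written, late event kept | 1 | 0 | 171 |
| Event-free completers censored at own EOS date, evenly spread over Days 161–175 | 31 | 0.785 × 30/31 = 0.760 | not reached |
| Events and censoring truncated at Day 168 | – | 0.785 | not reached |

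Two late events, on Days 170 and 173, give 0.785 × 1/2 = 0.393 and then 0, with a printed median of 170. Coding 24 weeks as Day 169 only moves the affected days to 170–175.

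**Step 3: when the median is affected.** With one event on Day 171 and S(168) = 0.893, 0.785, 0.685 or 0.576, the written rule prints 171, against not reached under censoring at the EOS date. At S(168) = 0.521, censoring at the EOS date also gives 171, so the median is not clearly wrong. At S(168) = 0.458 the median is Day 151 under both rules and only the tail of the curve is wrong.

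**Step 4: how likely a late event is.** Assume a constant first-event rate λ per year. Then P = 1 − exp(−m), where m = 124 × exp(−168λ/365.25) × (mean days after Day 168 per completer) × λ/365.25. With EOS uniform on Days 161–175 the mean is (1+2+…+7)/15 = 28/15 days. With EOS uniform on Days 165–171 it is (1+2+3)/7 = 6/7 day.

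| λ | Event-free at Day 168 | P, Days 161–175 | P, Days 165–171 |
|---|---|---|---|
| 0.3 | 0.871 | 15% | 7% |
| 0.5 | 0.795 | 22% | 11% |
| 1.0 | 0.631 | 33% | 17% |

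For example, at λ = 0.5 with the wider window, m = 124 × 0.795 × 1.867 × 0.5/365.25 = 0.252 and P = 22%. Simulation gave 15%, 23% and 33% for the wider window and 7%, 11% and 17% for the narrower one. If every visit falls by Day 168, P = 0. Only above about 1.5 events per year does S(168) fall below 0.5.

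**Step 5: unobserved time.** With visits uniform on Days 161–175, 7/15 of completers are seen on Days 161–167, on average 4 days early: 124 × 7/15 × 4 = 231 person-days. Against about 138 × 168 = 23,184, that is 1%.

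**The case against.** The strongest reply is that the plan already contains the cap. The censoring sentence speaks of participants with no exacerbation in the study period, Protocol 4.1 gives that period as 24 weeks, and 9.4.3 defines the proportion endpoint by "asthma exacerbation during the 24 week study period". On that reading a first event on Day 171 lies outside the period and is censored at 24 weeks, and the problem disappears. It also disappears if 24 weeks means the date of the Week 24 visit. Both readings are possible. Neither is stated for event times, and 8.3.1 points the other way, so the text allows two different outputs from the same data.

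The support for late counting is indirect. The ±7 days appear only in the laboratory section, and the follow-up in 8.3.1 is "defined as the time from enrolment to the date of EOS visit", with enrolment meaning consent, so it does not start when the time-to-event clock starts. That is correct. What matters here, however, is where follow-up ends, and the laboratory window is stated for the same EOS visit.

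A reader might also infer from the plus-1 count that even an on-time EOS visit lies beyond the censoring time. The documents do not support this: Table 1 puts the first dose on Day 1 and 8.1.3 puts EOS on Day 168, which is 168 on the plus-1 count.

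Finally, the study is descriptive, with no hypothesis, and SAP Table 14.2.2 prints the numbers with and without an exacerbation above the median, so an absurd median might be noticed. This limits the harm but does not settle the rule.

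**Conclusion.** The point holds as a conditional defect. As written, the rule fixes the censoring time and leaves event times open. If first events after Day 168 are kept, the drop of the curve to 0 is exact arithmetic. A spurious median of 169 to 175 days also needs an EOS visit after Day 168, a first event in those days, and S(168) above 0.5, with the contrast fading close to 0.5. The chance is roughly 7% to 33% for assumed rates of 0.3 to 1.0 per year and visits spread over ±3 to ±7 days. It is 0% if no visit is late.

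A reader might infer that the plan will produce a false median, or that the analysis cannot go ahead without the change. The documents support neither: a cap is a possible reading, and the endpoint is a descriptive secondary one in a single-arm safety study. The unobserved time credited to early-window completers is minor, about 1% of person-time. This should be fixed before the analysis is run, but it is not critical to the study.

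**What to change.** In Protocol 9.4.3 and SAP 6.3.2, state one horizon on one day count, by either route:

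- censor event-free participants at their actual EOS or last assessed date, counted as date minus first dose plus 1, and keep events to the same date; or
- truncate both at Day 168: time = min(event day, last assessed day, 168), with a first event after Day 168 censored at 168.

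Either route removes the artefact and the unobserved days. The first uses all observed follow-up; the second matches a strict 24-week period. The cost is one sentence in the text and one line of code, with no new data.
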